Appendix 4.	Hepatic Monitoring Tests for Treatment-Emergent Abnormality	49
Appendix 5.	Blood Sampling Summary	50
Appendix 6.	Neurological Examinations.....	51
Appendix 7.	Protocol Amendment H8H-MC-LAHT(c) Summary Safety, Tolerability, and Pharmacokinetics of Lasmiditan when Co- administered with Topiramate in Healthy Subjects	53

1. Protocol Synopsis

Title of Study:

Safety, Tolerability, and Pharmacokinetics of Lasmiditan when Co-administered with Topiramate in Healthy Subjects

Rationale:

Topiramate is indicated for prophylaxis of migraine and may be used concomitantly with lasmiditan in the intended patient population. Study H8H-MC-LAHT (LAHT) is being conducted to evaluate the safety, tolerability, and pharmacokinetics (PK) of lasmiditan when co-administered with topiramate in healthy subjects.

Objective(s)/Endpoints:

Objectives	Endpoints
Primary To evaluate the safety and tolerability of a single dose of lasmiditan in combination with topiramate in healthy subjects.	A summary of the number of treatment-emergent adverse events and serious adverse events.
Secondary To evaluate the PK of lasmiditan alone and in combination with topiramate in healthy subjects. To evaluate the PK of topiramate alone and in combination with lasmiditan.	Maximum observed drug concentration (C_{max}), time of C_{max} (t_{max}), area under the concentration versus time curve from zero to last, and zero to infinity C_{max} , t_{max} , and area under the concentration versus time curve during 1 dosing interval

Summary of Study Design:

Study LAHT is a parallel, placebo-controlled, fixed-sequence study that assesses the safety, tolerability, and potential for PK interaction between investigator- and subject-blind lasmiditan/placebo and open-label topiramate.

A single dose of lasmiditan (200 mg) or placebo will be administered on the morning of Day 1. Topiramate 25 mg once daily (Day 3), 25 mg twice daily (BID) (Days 4 to 7), 50 mg BID (Days 8 to 13), followed by a single 50-mg dose on the morning of Day 14 will be administered. A single dose of lasmiditan (200 mg) or placebo will be co-administered with topiramate (50 mg) on the morning of Day 14.

Treatment Arms and Planned Duration for Subjects:

Screening Period: All subjects will participate in a screening visit of up to 28 days.

Treatment period: The subjects will be admitted to the clinical research unit (CRU) on the day before dosing (Day -1). Subjects will be discharged from CRU on Day 16 when all study procedures have been completed.

Follow-up period: Subjects will be discharged from the study approximately 10 days after the last dose of topiramate.

Number of subjects:

Approximately 30 subjects may be enrolled so that at least 21 complete the study.

Statistical Analysis:

Safety parameters that will be assessed include safety laboratory parameters, vital signs, neurological examination, Columbia Suicide Severity Rating Scale, and 12-lead electrocardiogram parameters. The parameters will be listed, and summarized using standard descriptive statistics, as appropriate.

Pharmacokinetic parameter estimates for lasmiditan, its metabolites, and topiramate will be calculated using standard noncompartmental methods of analysis. The parameters will be listed, and summarized using standard descriptive statistics, as appropriate.

Pharmacokinetic parameters will be evaluated to determine the impact of topiramate co-administration on the PK of a single dose of lasmiditan and its metabolites. Log-transformed C_{max} and area under the concentration versus time curve parameters will be evaluated in a linear mixed-effects model with fixed effects for treatment (lasmiditan co-administered with topiramate [Day 14; test treatment] versus lasmiditan alone [Day 1; reference treatment]), and a random effect for subject. The treatment differences will be back-transformed to present the ratios of geometric means and the corresponding 90% confidence interval (CI).

A similar analysis will be performed to determine the impact of co-administration of a single dose of lasmiditan on the steady-state PK of topiramate. The model will include the following treatments: topiramate co-administered with lasmiditan (Day 14; test treatment) versus topiramate alone (Day 13; reference treatment).

The t_{max} will be analyzed using the Wilcoxon signed rank test. Estimates of the median difference based on the observed medians, 90% CIs, and p-values from the Wilcoxon test will be calculated.

2. Schedule of Activities

Study Schedule Protocol H8H-MC-LAHT

	Screening	-1	Study Days															Discharge	Follow-up/ED	Comments
			1	2	3	4	5	6	7	8	9	10	11	12	13	14	15			
Procedure	-28 to -2 days prior to Day 1																Day 16	~10 days after last dose		
Informed Consent	X																			
Subject Admission to CRU		X																		
Subject Discharge from CRU																	X			
Lasmiditan/Placebo Administration			X Day 1, indicates Time = 0													X				
Topiramate Administration					X	X	X	X	X	X	X	X	X	X	X			25 mg QD on Day 3, 25 mg BID from Day 4 to 7, 50 mg BID from Day 8 to 13, a single 50-mg dose on the morning of Day 14		
Neurological Examination		X	X		X	X			X					X	X		X	On dosing days, all time points predose and 4-hour postdose for morning dose only. Day 3 is predose only. Non-		

	Screening		Study Days														Discharge	Follow-up/ED	Comments	
Procedure	-28 to -2 days prior to Day 1	-1	1	2	3	4	5	6	7	8	9	10	11	12	13	14	15	Day 16	~10 days after last dose	
																			dosing days at single time point.	
C-SSRS/Self-Harm	X	X																X	X	
Medical History	X																			
Height	X																			
Weight		X															X		Body weight should be recorded on Day -1 of all study periods.	
Vital Signs (supine)			0, 2, 4, 8 h	24 h	0 & 2 h	0 & 2 h		0 & 2 h			0, 2, 4, 8 h	0, 2, 4, 8 h	24 h						On dosing days, time points correspond to morning dose only. Day 3 time points at evening dose.	
	X	X															X	X	Time points may be added for each study period, if warranted and agreed upon between Lilly and the investigator.	

	Screening		Study Days														Discharge	Follow-up/ED	Comments	
Procedure	-28 to -2 days prior to Day 1	-1	1	2	3	4	5	6	7	8	9	10	11	12	13	14	15	Day 16	~10 days after last dose	
																				Triplicate BP monitoring
Orthostatic Blood Pressure	X		0, 2, & 4 h												0, 2, & 4 h	0, 2, & 4 h			Day 13 time points at morning dose only.	
Clinical Laboratory Tests	X	X						X							X			X		See Appendix 2 , Clinical Laboratory Tests, for details.
Pregnancy Test		X																X		Serum pregnancy test will be performed at screening. Urine pregnancy test will be performed at every admission period and at poststudy, if applicable.

	Screening		Study Days															Discharge	Follow-up/ED	Comments
Procedure	-28 to -2 days prior to Day 1	-1	1	2	3	4	5	6	7	8	9	10	11	12	13	14	15	Day 16	~10 days after last dose	
Physical Examination	X	X			Predose													X		After screening, medical assessment is performed only to include medical review and targeted examination, as appropriate.
12-Lead ECG	X		Predose		X	X			X					X	X		X		Single; all at predose for morning dose only.	
AE/Medication Review	X	X	X	X	X	X	X	X	X	X	X	X	X	X	X	X	X			
Lasmiditan and Metabolite PK Samples			Predose, 0.5, 1, 1.5, 2, 3, 4, 6, 8, 12 h	24, 36 h	48 h											Predose, 0.5, 1, 1.5, 2, 2.5, 3, 4, 6, 8, 12 h	24, 36 h	48 h		
Topiramate PK Samples															Predose, 0.5, 1, 1.5, 2, 3, 4, 6, 8, 12 h	Predose, 0.5, 1, 1.5, 2, 3, 4, 6, 8, 12 h			Time points at morning dose only.	
Genetic Sample		X																		

Abbreviations: BID = twice daily; BP = blood pressure; CRU = clinical research unit; C-SSRS = Columbia Suicide Severity Rating Scale; ECG = electrocardiogram; ED = early discontinuation; h = hour; min = minutes; PK = pharmacokinetics; QD = once daily.

Note: if multiple procedures take place at the same time point, the following order of the procedure should be used: ECG, vital signs, and venipuncture.

3. Introduction

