3.2. Background

Across the completed Phase 1, 2, and 3 clinical studies, doses of 0.1 to 400 mg of lasmiditan were evaluated in healthy subjects or patients with migraine. To date, lasmiditan has been administered to 230 healthy subjects and to 1632 patients with migraine. Compared with placebo, the most frequently reported lasmiditan treatment-emergent adverse events (TEAEs) included dizziness, paresthesia, somnolence, fatigue, lethargy, and nausea. The majority of these

TEAEs were mild or moderate in severity and none led to subject withdrawal. One patient experienced a serious adverse event (SAE) of dizziness that was moderate in severity (lasmiditan 200 mg).

Oral tablet doses of lasmiditan up to 400 mg did not result in any clinically relevant changes in electrocardiograms (ECGs) (including QT interval/corrected QT interval [QTc]) following administration to healthy subjects. In the thorough QT study in healthy subjects, no clinically significant changes in blood pressure, heart rate, or 12-lead ECG were observed at the 100- or 400-mg single-dose levels. Lasmiditan caused no significant QT prolongation at either dose.

In healthy subjects, peak plasma concentrations of lasmiditan were observed approximately 1 to 2.5 hours after a single oral dose ranging from 25 to 400 mg, and the geometric mean terminal half-life was approximately 4 to 6 hours. Lasmiditan exhibited dose-linear PK; low to moderate intersubject variability in exposure was observed across doses (% coefficient of variation up to 61% and 45% for maximum observed drug concentration [C_{max}] and area under the concentration versus time curve [AUC], respectively). Co-administration of lasmiditan with a high-fat diet led to a delay in median time of maximum observed drug concentration (t_{max}) value by approximately 1 hour and a modest (~20%) increase in lasmiditan C_{max} and AUC values, relative to that under fasted conditions.

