3.3. Benefit/Risk Assessment

The primary objective of this study is to evaluate the safety and tolerability of a single dose of lasmiditan in combination with topiramate in healthy subjects. There is no anticipated therapeutic benefit for the subjects.

No clinically significant safety or tolerability concerns have been identified in subjects to date for lasmiditan up to the highest single oral dose given (400 mg). Dosing of lasmiditan in this study will be conducted in an inpatient setting, and subjects will be monitored in the clinical research unit (CRU) for at least 48 hours after dosing.

More information about the known and expected benefits, risks, SAEs, and reasonably anticipated AEs of lasmiditan is to be found in the Investigator's Brochure (IB).

Topiramate is a marketed drug and will be administered within a dose titration regimen that has been tolerated in previous PK studies in healthy subjects (e.g. Bialer et al. 2013; Manitpisitkul et al. 2014a,b).

More detailed information about the known and expected benefits and risks of topiramate may be found in the following: 2017 US Prescribing Information.

4. Objectives and Endpoints

Table LAHT.1 shows the objectives and endpoints of the study.

Table LAHT.1. Objectives and Endpoints

Objectives	Endpoints
Primary To evaluate the safety and tolerability of a single dose of lasmiditan in combination with topiramate in healthy subjects.	A summary of the number of treatment-emergent adverse events and serious adverse events
Secondary To evaluate the pharmacokinetics of lasmiditan alone and in combination with topiramate in healthy subjects.	C_{max} , t_{max} , $AUC(0-t_{last})$ and $AUC(0-\infty)$
To evaluate the pharmacokinetics of topiramate alone and in combination with lasmiditan.	C_{max} , t_{max} , and AUC_{τ}
Exploratory To evaluate the pharmacokinetics of lasmiditan metabolites alone and in combination with topiramate in healthy subjects.	C_{max} , t_{max} , $AUC(0-t_{last})$, and $AUC(0-\infty)$

Abbreviations: $AUC(0-t_{last})$ = area under the concentration versus time curve from time zero to time t , where t is the last time point with a measurable concentration; $AUC(0-\infty)$ = area under the concentration versus time curve from zero to infinity; AUC_{τ} = area under the concentration versus time curve during 1 dosing interval; C_{max} = maximum observed drug concentration; t_{max} = time to C_{max} .

5. Study Design

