9.5. Pharmacokinetics

At the visits and times specified in the Schedule of Activities, venous blood samples of approximately 3 mL each will be collected to determine the plasma concentrations of lasmiditan and its metabolites. Similarly, at times specified in the Schedule of Activities, 2 mL of venous blood samples will be collected to determine the plasma concentrations of topiramate. A maximum of 3 samples may be collected at additional time points during the study if warranted and agreed upon between both the investigator and sponsor. Instructions for the collection and handling of blood samples will be provided by the sponsor. The actual date and time (24-hour clock time) of each sampling will be recorded.

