10.1. Sample Size Determination

Approximately 30 subjects will be enrolled, so that at least 21 subjects complete the study. Subjects will be randomized in a 2:1 ratio of lasmiditan 200 mg:placebo. The sample size is customary for Phase 1 studies evaluating safety and tolerability, and is not powered on the basis of statistical hypothesis testing.

Subjects who are randomized but who do not complete Day 14 treatment may be replaced to ensure that enough subjects complete the study.

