- Actual sampling times will be used in the final analyses of individual PK parameters, except for non-bolus pre-dose sampling times which will be set to zero. For non-bolus, multiple dose profiles, the pre-dose time will be set to zero unless a time deviation falls outside of the protocol blood collection time window which is considered to impact PK parameter derivation.
- C_{\max} and t_{\max} will be reported from observed values. If C_{\max} occurs at more than one time point, t_{\max} will be assigned to the first occurrence of C_{\max} .
- AUC parameters will be calculated using a combination of the linear and logarithmic trapezoidal methods (linear-log trapezoidal rule). The linear trapezoidal method will be applied up to t_{\max} and then the logarithmic trapezoidal method will be used after t_{\max} . The minimum requirement for the calculation of AUC will be the inclusion of at least three consecutive plasma concentrations above the lower limit of quantification (LLOQ), with at least one of these concentrations following C_{\max} . AUC(0-∞) values where the percentage of the total area extrapolated is more than 20% will be flagged. Any AUC(0-∞) value excluded from summary statistics will be noted in the footnote of the summary table.
- Half-life ($t_{1/2}$) will be calculated, when appropriate, based on the apparent terminal log-linear portion of the concentration-time curve. The start of the terminal elimination phase for each subject will be defined by visual inspection and generally will be the first point at which there is no systematic deviation from the log-linear decline in plasma concentrations. Half-life will only be calculated when a reliable estimate for this parameter can be obtained comprising of at least 3 data points. If $t_{1/2}$ is estimated over a

time window of less than 2 half-lives, the values will be flagged in the data listings. Any $t_{1/2}$ value excluded from summary statistics will be documented in the footnote of the summary table.

- A uniform weighting scheme will be used in the regression analysis of the terminal log-linear portion of the concentration-time curve.
- The parameters based on predicted C_{last} will be reported.

Individual PK Parameter Rules

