9.3.2 Pharmacokinetic Statistical Methodology

PK parameters will be evaluated to determine the impact of topiramate co-administration on the PK of a single dose of lasmiditan and its metabolites. Log-transformed C_{max} , $AUC(0-\infty)$, and $AUC(0-t_{last})$ parameters will be evaluated in a linear mixed-effects model with fixed effects for treatment and a random effect for subject. The treatment differences will be back-transformed to present the ratios of geometric means and the corresponding 90% confidence interval (CI). The comparison of interest is:

Lasmiditan co-administered with topiramate (Day 14; test treatment) versus Lasmiditan alone (Day 1; reference treatment)

An example of the SAS code that will be used is as follows:

```
proc mixed data=xxx;
  class trtmnt subject;
  model l_pk = trtmnt / alpha=0.1;
  random subject;
  lsmeans trtmnt / pdiff;
run;
```

where l_pk is the log-transformed (base e) PK parameter.

A similar analysis will be performed to determine the impact of co-administration of a single dose of lasmiditan on the steady-state PK of topiramate. This analysis shall evaluate the log-transformed C_{max} and AUC_{τ} using a similar model to the one described above. The comparison of interest will be:

Topiramate co-administered with lasmiditan (Day 14; test treatment) versus Topiramate alone (Day 13; reference treatment)

The t_{max} will be analyzed using the Wilcoxon signed rank test. Estimates of the median difference based on the observed medians, 90% CIs and p-values from the Wilcoxon test will be calculated.

Additional analyses may be performed, as warranted.

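### Lasmiditan is sampled at 2.5 h on Day 14 but not on Day 1, and no rule equalises the grids, so the Cmax ratio is biased slightly upward and the median tmax can shift

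*Protocol*

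**What the plan says.** The lasmiditan and metabolite row of Protocol Section 2 schedules these draws over the first 12 hours:

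- Day 1, lasmiditan alone: "Predose, 0.5, 1, 1.5, 2, 3, 4, 6, 8, 12 h"
- Day 14, lasmiditan with topiramate: "Predose, 0.5, 1, 1.5, 2, 2.5, 3, 4, 6, 8, 12 h"

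Both days continue with draws at 24, 36 and 48 h. Protocol Section 3.2 reports that "peak plasma concentrations of lasmiditan were observed approximately 1 to 2.5 hours after a single oral dose".

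SAP 9.3.1 (General PK Parameter Rules) says that Cmax and tmax "will be reported from observed values". SAP 9.3.2 compares Day 14 with Day 1. Log Cmax and log AUC go into a mixed model that yields a ratio of geometric means with a 90% CI. For tmax the SAP uses the Wilcoxon signed rank test, with "Estimates of the median difference based on the observed medians".

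Protocol Section 9.5 leaves room for unscheduled draws: "A maximum of 3 samples may be collected at additional time points during the study if warranted", if investigator and sponsor agree.

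Lasmiditan Cmax and tmax are secondary endpoints (Protocol Section 4). The metabolites share the grid under an exploratory objective, "To evaluate the pharmacokinetics of lasmiditan metabolites alone and in combination with topiramate in healthy subjects".

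**The concern.** The test-day maximum is taken over one more near-peak draw than the reference-day maximum. A scheduled tmax of 2.5 h can occur only on Day 14. Part of any reported rise in Cmax, and possibly a step in median tmax, would then come from the schedule and not from topiramate.

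Neither document deals with this. The sampling-window rules in SAP 9.3.1 apply only to average concentration profiles, and using actual sampling times does not supply a missing Day 1 draw. The topiramate comparison does not have the problem, because its grids on Days 13 and 14 are identical. The documents give no reason for treating lasmiditan differently.

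Protocol Section 3.1 rates an interaction as very unlikely, so a ratio close to 1 is the expected result, and that is where a shift made by the schedule is least welcome.

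**Working it through.** **1. Is the asymmetry real?** Count the scheduled draws.

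- Day 1: 10 up to 12 h, plus 3 later = 13
- Day 14: 11 up to 12 h, plus 3 later = 14
- Total: 13 + 14 = 27, the figure in Protocol Appendix 5

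A 2.5 h draw on both days would give 28, and on neither day 26. Appendix 7 prints the same two grids. The difference is therefore in the plan and not a fault of text extraction.

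**2. Direction.** Let M be the maximum over the common grid and C(2.5) the extra concentration. The Day 14 observed Cmax is max(M, C(2.5)). With no interaction, the bias in the log ratio is E[max(0, ln C(2.5) − ln M)]. This cannot be negative, and it is zero if the 2.5 h value is left out.

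**3. One profile by hand.** Take a one-compartment oral model (assumed), half-life 5 h (Protocol Section 3.2 gives 4 to 6 h), true tmax 2.5 h and no noise.

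- ke = ln 2 / 5 = 0.1386 per h
- ka solves ln(ka/ke)/(ka − ke) = 2.5, so ka = 0.876 per h
- C(t) is proportional to exp(−ke·t) − exp(−ka·t): 0.5845 at 2 h, 0.5952 at 2.5 h, 0.5876 at 3 h

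Day 1 would record 0.5876 at 3 h and Day 14 would record 0.5952 at 2.5 h. The ratio is 0.5952/0.5876 = 1.013, and tmax falls from 3.0 to 2.5 h with no interaction. For a true tmax of 2 h without noise the extra draw changes nothing, so the size depends on how tmax and noise are spread.

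**4. Averaging over subjects.** This is a simulation with no interaction: 400,000 profiles in each of 16 scenarios. Assumptions not in the documents are the one-compartment shape, a 30% between-subject spread in tmax, and independent sample-to-sample noise of 0 to 20%. Half-life is 5 h. Inflation of the Cmax ratio:

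| Typical tmax | 0% noise | 5% | 10% | 20% |
|---|---|---|---|---|
| 1 h | 0.0% | 0.1% | 0.3% | 1.1% |
| 1.5 h | 0.1% | 0.4% | 1.0% | 2.1% |
| 2 h | 0.2% | 0.9% | 1.6% | 2.8% |
| 2.5 h | 0.2% | 1.1% | 1.9% | 3.0% |

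On the common grid the bias is 0.0% throughout. Where there is noise, 2 to 10% of Day 14 profiles peak at 2.5 h when typical tmax is 1 h, and 12 to 26% when it is 1.5 to 2.5 h. Varying half-life over 4 to 6 h, absorption variability and lag time raises the 20%-noise figures to about 1.4, 2.3, 3.1 and 3.5% for the four tmax values. AUC changes by less than 0.1%.

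**5. tmax.** Across all simulated profiles, the median is unchanged in 11 of the 16 scenarios. It moves from 3.0 to 2.5 h in the four with typical tmax 2.5 h, and from 1.5 to 2.0 h in one (1.5 h, 20% noise). Mean tmax moves by less than 0.1 h.

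The reported figure, however, is a median of 14 to 20 subjects: two thirds of 21 completers or of 30 enrolled. The share of simulated trials in which adding the 2.5 h value moves the Day 14 median by 0.5 h or more is about:

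| Typical tmax | Up | Down |
|---|---|---|
| 1 h | 0–9% | never |
| 1.5 h | 0–18% | almost never |
| 2 h | 1–27% | 0–7% |
| 2.5 h | 15–29% | 18–50% |

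The rejection rate of the signed rank test at nominal 0.10, with an assumed 20% occasion-to-occasion variation in tmax, is 0.098 to 0.129 on the planned grids and 0.098 to 0.105 on the common grid.

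**6. Scale against the CI.** SE of the log ratio = sqrt(2·ln(1 + CV²)/n), with an assumed within-subject CV of 20 or 30%. The 90% CI around a ratio of 1 is exp(±t·SE).

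- n = 14, t = 1.771: SE 0.0749 or 0.1110; CI 0.88–1.14 or 0.82–1.22
- n = 20, t = 1.729: SE 0.0626 or 0.0928; CI 0.90–1.11 or 0.85–1.17

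From the noncentral t distribution, a 1% bias leaves coverage at 89.6 to 89.9%, and a 3% bias leaves it at 86.5 to 88.9%, against 90% nominal.

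**The case against.** The strongest objection is materiality. PK is secondary, the trial "is not powered on the basis of statistical hypothesis testing", no equivalence limits are stated for a 1% shift to cross, and the bias is small against the CI. That stands, and it is why this is an optional improvement.

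The sizes also rest on assumptions. The 3% end needs 20% independent noise and a typical tmax of 2 to 2.5 h, the later part of a window that pools doses from 25 to 400 mg. At 5% noise the bias is at most 1.1%. The tmax step is a possibility and not the expected result: downward steps arise essentially only when typical tmax is about 2 h or later, and with an even number of subjects the step may be 0.25 h. These qualifications are fair, but none touches the asymmetry or the direction of the Cmax bias.

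Both documents allow further analyses if warranted, so a common-grid analysis could be added later. That is permission and not a rule, and it leaves the handling of the 2.5 h value to be chosen after the data are seen.

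Finally, the common grid discards a valid observation near the peak. Reporting both results answers that.

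**Conclusion.** The concern holds. The unequal grid is certain from the documents, and so is the upward direction of the Cmax bias when there is no interaction. The size, about 0 to 1% for a typical tmax of 1 h and 0 to 3% for 1.5 to 2.5 h, depends on the assumed model, tmax spread and noise. A 0.5 h step in the reported median tmax is possible in either direction.

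This is minor. It is unlikely to alter the interaction conclusion alone, it leaves AUC practically unchanged, and it does not touch the primary safety objective. For the metabolites no size can be given, because the documents state no metabolite tmax.

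**What to change.** Preferred: schedule identical lasmiditan sampling times on Days 1 and 14. This takes a small protocol amendment. If investigator and sponsor agree, one of the additional samples in Protocol Section 9.5 could serve, although that provision does not schedule a draw for every subject.

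If the schedule stays, add one sentence to SAP 9.3: the Day 14 versus Day 1 comparison of Cmax and tmax for lasmiditan and its metabolites omits the 2.5 h sample, and the full-grid results are reported alongside. The cost is one rerun, with one valid Day 14 sample left out of one of the two analyses.

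A separate clerical matter is footnote b of Appendix 5. It says that the counts include 3 potential extra samples, but the scheduled draws alone already make 27 for lasmiditan and 10 + 10 = 20 for topiramate. The footnote and the counts should be reconciled.
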